9.3.4 Image Transfer

Only the MRI scans specified below for the two strata will be electronically transferred to the PBTC to be submitted to the PBTC Neuroimaging Center (NIC). All subject specific data will be stripped from the images and will be replaced with PBTC Accession numbers by the PBTC prior to sending images to the NIC. All image data transfer is accomplished using PGP (pretty-good-privacy) 128-bit encryption, which meets industry standard for secure communication.

Stratum I:

All imaging studies obtained during the first 9 courses of treatment (approximately 1 year) will be centrally reviewed by the NIC. In addition if they occur beyond the first 9 courses of treatment imaging studies documenting smallest disease measurement recorded since the start of protocol, responses, confirmation of responses (follow-up scan approximately 3 months later) and documenting PD will also centrally reviewed and the protocol criteria for disease assessment will be compared to the MacDonald criteria.

Stratum II:

Central review of imaging studies will be carried out only in patients with a response or progressive disease while on study. For these patients, central review of smallest disease measurement recorded since the start of protocol, imaging studies documenting responses, confirmation of responses (follow-up scan approximately 3 months later) and studies documenting PD will be carried out and the protocol criteria for disease assessment will be compared to the MacDonald criteria.

10 STUDY CALENDAR

Table 2 Standard Clinical and Laboratory Assessments

| | Pre- Therapy | Course 1 | Course 2-9 | Course 10-18 | End of Treatment |
|--|---------------------------|----------------|----------------|---------------------------|---------------------|
| PHYSICAL ASSESSMENTS | | | | | |
| Complete History | X | | | | |
| Interval History | | X ^A | X ^C | $\mathbf{X}^{\mathbf{F}}$ | X |
| Psychiatric History** | X | X ^A | XC | $\mathbf{X}^{\mathbf{F}}$ | X |
| Performance status | X | X ^A | X ^C | $\mathbf{X}^{\mathbf{F}}$ | X |
| Physical including neurologic exam | X | X ^A | X ^C | $\mathbf{X}^{\mathbf{F}}$ | X |
| Visual field evaluation (as feasible) | X | | X ^C | $\mathbf{X}^{\mathbf{F}}$ | |
| Ophthalmology evaluation | X | | X ^C | $\mathbf{X}^{\mathbf{F}}$ | |
| Vital signs | X | X ^A | X ^C | $\mathbf{X}^{\mathbf{F}}$ | X |
| LABORATORY EVALUATION | | | | | |
| CBC (WBC, Hgb, Hct, Platelets, ANC, ALC) | X | X ^A | XC | \mathbf{X}^{F} | X |
| Serum Chemistries (Electrolytes, BUN, Creatinine, SGOT(AST), SGPT(ALT), Total Bilirubin, TSH | X | X ^A | X ^C | X ^F | X |
| Urinalysis for protein (Urine Dip) | X | X ^A | X ^C | X ^F | X |
| Serum or urine pregnancy test (for females of childbearing potential) | X | X ^C | X ^C | X ^F | |
| IMAGING EVALUATION | | | | | |
| Brain MRI with thin cuts through the sella ^D | X | | X^B | $\mathbf{X}^{\mathbf{G}}$ | X |
| OTHER | | | | | |
| Biology Studies (assessment of WNT and MAPK pathway activation) | $\mathbf{X}^{\mathbf{E}}$ | | | | |
| FFPE tumor tissue for PBTC CRB | X^{E} | | | | |
| PBMC for PBTC CRB | X^{E} | | | | |

- Assessments should be done prior to starting course 2, i.e. prior to the 7th injection.
- B Obtain every 12 weeks at time of visit and at time of progression as feasible
- C Obtain every 12 weeks at time of visit
- D See section 9.3 9.3.1
- E See section 9.1.
- F Obtain every 18 weeks at time of visit
- Obtain every 18 weeks at time of visit and at time of progression as feasible

^{*} NOTE: Patients who do not have a Brain MRI performed at or after 9 courses (approximately 12 months) will be considered failures for the purpose of assessing the primary objective according to the statistical design. See section 13.4.1.

** Psychiatric History: patient/family will be queried about mood, depression and suicidal ideations at each study visit. If there are any concerns about significant depression or any suicidal ideation, patient should be referred to Psychiatrist.

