9.3.3 Timing of Assessment

Imaging studies will be done at baseline prior to PEGINTERFERON ALFA-2B therapy and every 12 weeks for the first 9 courses (approximately 1 year) then every 18 weeks thereafter until subjects develop evidence of disease progression, unacceptable toxicity or completion of 18 courses (approximately 2 years) of PEGINTERFERON ALFA-2B therapy.

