13 STATISTICAL CONSIDERATIONS

13.1 Primary Endpoints

Stratum 1: Rate of disease stabilization for 1 year (i.e. 9 courses of treatment).

Stratum 2: Sustained Objective Response (PR+CR) rate in the cystic and/or soft tissue component observed during the first year of treatment (i.e. 9 courses of treatment). Response must be sustained for 3 months.

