Objective response (CR+PR) rate observed during the first year of treatment (more specifically during the first 9 courses) is the primary endpoint for this stratum. In order to count towards the success criteria, objective responses observed during the first year must be sustained for 3 months. Simon's optimal two-stage design will be employed in this stratum, where accrual will stop, i.e. the trial will terminate early if evidence accumulates that the efficacy is lower than the specified acceptable levels. For patients who have failed radiation, >10% response rate will be the minimal acceptable threshold for response, but > 35% will be the threshold to establish efficacy. More specifically PEGINTERFERON ALFA-2B will be deemed not worthy of further investigation in this patient population if the true sustained objective response (CR+PR) rate during the first year of treatment is less than 10% and the design will have 90% statistical power for a true response rate of 35%. These parameter settings coupled with type I and II error rates set at 10% lead to a sample size of 19 eligible and evaluable patients based on a Simon's optimal design. Eleven (11) patients will be accrued in the first stage and if one (1) or fewer sustained objective responses are observed among the first 11 patients during their 1st year of treatment, the stratum will be closed to accrual and we will conclude that PEGINTERFERON ALFA-2B does not merit continued investigation in this disease due to lack of efficacy. Otherwise accrual will continue until 19 evaluable patients have been treated and assessed for objective response and toxicity. If four or more (≥ 4) patients experience sustained objective responses (CR+PR), then

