13.4.1 Definition of Evaluable Patients

In both strata, all patients who receive at least 1 dose of PEGINTERFERON ALFA-2B will be considered evaluable for the purposes of assessing the primary objectives of this trial.

In both strata, patients who withdraw, are lost to follow-up, and/or are removed from treatment and who fail to be evaluated for the primary outcome will be counted as failures.

REFERENCES

- **2.** Rubinstein LJ RD. *Pathology of Tumours of the Nervous System.* 5 ed. Baltimore: Williams & Wilkie; 1990.

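### The Table 2 note on a missing 9-course MRI names no stratum and so contradicts the Stratum 2 success rule and Section 13.4.1 for a response confirmed before the end of course 9

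*Combined protocol and SAP*

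**What the plan says.** Four places bear on how a Stratum 2 patient is scored.

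- **Section 10, Table 2 note.** "Patients who do not have a Brain MRI performed at or after 9 courses (approximately 12 months) will be considered failures for the purpose". The note then gives its purpose as that "of assessing the primary objective according to the statistical design. See section 13.4.1". The calendar serves both strata and the note names neither.
- **Section 13.1.** The Stratum 1 endpoint is "Rate of disease stabilization for 1 year (i.e. 9 courses of treatment"). The Stratum 2 endpoint is a sustained CR or PR "observed during the first year of treatment (i.e. 9 courses of treatment). Response must be sustained for 3 months".
- **Section 13.3, Stratum 2.** "In order to count towards the success criteria, objective responses observed during the first year must be sustained for 3 months". Neither 13.1 nor 13.3 asks for a scan at 1 year in this stratum.
- **Section 13.4.1, both strata.** Patients who withdraw, are lost, or "are removed from treatment and who fail to be evaluated for the primary outcome will be counted as failures".

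On imaging, Section 9.3.3 schedules MRI every 12 weeks for the first 9 courses and every 18 weeks after that, "until subjects develop evidence of disease progression, unacceptable toxicity or completion of 18 courses".

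**The concern.** The note's condition is natural for Stratum 1: without imaging at the end of the year, stabilization for the year cannot be shown. The Stratum 2 endpoint is not status at 1 year. It is an event that can be complete months earlier, and once the 3-month follow-up scan has confirmed it, no later scan adds to the definition.

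An analyst who follows the note would in effect replace sustained response within the first year by sustained response plus imaging at or after 1 year. The Stratum 2 cut-offs (stop at 1 or fewer of 11; success at 4 or more of 19) and the stated 90% power belong to the first definition. The effect could only lower the observed rate. An analyst who follows Section 13 would score the same patient as a success. In a single-arm stratum of 19, that choice should not be left open until outcomes are known.

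**Working it through.** **Step 1. Can the Stratum 2 endpoint be complete before the note's time point?** A course is 6 weeks (Section 5.1), so 9 courses take 9 × 6 = 54 weeks. Scans every 12 weeks fall at weeks 12, 24, 36 and 48. A response first seen at week 12, 24 or 36 can be confirmed about 3 months later, at week 24, 36 or 48, always before week 54. A response first seen at week 48 is confirmed at about week 60, and that scan itself satisfies the note.

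**Step 2. Can such a patient lack a later MRI?**

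- *Progression, another therapy or withdrawal of consent before about week 54.* These take the patient off study (Section 5.5), and disease status after that date is not collected (Section 5.5.1). Progression is measured from the smallest measurement on study (Section 11.1.3), so a confirmed responder can progress. These are the firm routes.
- *Stopping treatment for toxicity or by refusal.* These are off-treatment reasons (Section 5.3.2). Sections 5.4.2 and 5.4.3 keep the patient in follow-up but set no MRI dates. A missing scan is possible, not automatic.

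**Step 3. Score that patient under each rule.**

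| Rule | Score of a confirmed early responder with no MRI at or after 9 courses |
|---|---|
| 13.1 and 13.3, Stratum 2 | Success: response in the first 9 courses, sustained 3 months |
| 13.4.1 | Not failed: the primary outcome was evaluated |
| Table 2 note, as worded | Failure |

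**Step 4. Reproduce the plan's design.** Inputs from Section 13.3 and Table 4: n1 = 11, stop if 1 or fewer; n = 19, success if 4 or more; rates 10% and 35%.

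- P(stop at stage 1) = (1−p)^11 + 11p(1−p)^10
- P(success) = Σ over x = 2 to 11 of P(X1 = x) · P(X2 ≥ 4−x), with X1 ~ Bin(11, p) and X2 ~ Bin(8, p)

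At p = 0.10, early stopping is 0.697 and type I error 0.099. At p = 0.35, early stopping is 0.061 and power 0.909. These agree with the stated 70%, 6%, 10% and 90%.

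**Step 5. Effect if the note were applied.** Let d be the share of sustained responders with no MRI at or after 9 courses. The documents give no value, so d is an assumption. The scored rate is p × (1−d).

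| d (assumed) | Scored rate at true 35% | Power | False early stop | Scored rate at true 10% | Type I error |
|---|---|---|---|---|---|
| 0 | 35.0% | 0.909 | 0.061 | 10.0% | 0.099 |
| 5% | 33.25% | 0.883 | 0.076 | 9.5% | 0.085 |
| 10% | 31.5% | 0.852 | 0.094 | 9.0% | 0.073 |
| 20% | 28.0% | 0.772 | 0.142 | 8.0% | 0.051 |

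The row d = 0 is also the result for any d if Section 13 is followed.

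**The case against.** The strongest reply is that the note does not stand alone. It ends by deferring to the statistical design and to Section 13.4.1, which fails only those "who fail to be evaluated for the primary outcome will be counted as failures". A confirmed responder was evaluated. The note also speaks of one primary objective where Section 1.1 lists two, and its time point matches only the Stratum 1 endpoint. Its asterisk has no visible anchor in the extracted table, so a limiting position may have been lost in reading the PDF. All this makes a Stratum 1 intention likely. It does not settle the matter: the note states its own failure criterion, that criterion differs from the one it cites, and no text gives either precedence.

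A reader might infer that confirmed Stratum 2 responders *do* become failures under this plan. The documents do not support that, because the section to which the note points would not fail them. A reader might also infer that stopping for toxicity or refusal by itself removes the later scan. Section 5.4.2 requires continued follow-up and data, so it does not.

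The affected group is further narrowed because isolated cystic enlargement is not progression in Stratum 2 during the first 12 months (Section 11.1.3). Two further replies stand: the documents support no particular value of d, and any design with a cut-off of 4 of 19 is sensitive to one patient.

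**Conclusion.** The plan holds an unresolved contradiction in the scoring of the Stratum 2 primary endpoint. It is not a settled analysis that fails responders. It affects patients whose response is confirmed by weeks 24 to 48 and who then progress, start another therapy or withdraw consent before about week 54, or who stop treatment and happen to have no later scan.

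The cost in power and in false early stopping shown above arises only if the note is applied over Section 13, and its size depends wholly on the assumed d. Under that reading even d = 5% takes power below the stated 90%. The bias is conservative, since type I error falls as well. It would be wrong to conclude that Stratum 2 is underpowered as designed: under Section 13 its operating characteristics stand as stated. The point should be fixed because the ambiguity concerns a primary endpoint and is easy to remove; it does not put the design in doubt.

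**What to change.** Limit the Table 2 note to Stratum 1. Add that in Stratum 2 a CR or PR first seen in courses 1 to 9 and sustained on the 3-month follow-up scan is a success whether or not an MRI is done at or after 9 courses, and that a patient without such a documented response is a failure. Section 13.4.1 is already consistent with this and needs at most a clarifying sentence.

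The cost is one or two sentences in an amendment. No scans, patients or staff time are added, and the sample size, cut-offs and stated error rates do not change.

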11 MEASUREMENT OF EFFECT

Response will be assessed on MRI scans, neurologic examinations and visual field evaluations when applicable. Best response will be defined as below, based on the definitions used in the pilot study of non-pegylated interferon¹⁵:

11.1 Tumor Response Criteria

Please note, measurements are required for both the solid and cystic components

11.1.1 Complete response (CR):

Total disappearance of all radiographically detectable tumor. Response must be sustained on the follow-up scan 3 months later.

11.1.2 Partial response (PR):

At least 50% decrease in the product of the greatest perpendicular diameters of the tumor as a whole, i.e., solid and cystic components. Response must be sustained on the follow-up scan 3 months later.

11.1.3 Progressive disease (PD):

The definitions of PD vary by strata and time on treatment given that transient increases in cyst size can be seen both during interferon therapy as well as for a prolonged period of time after radiation therapy.

Stratum 1:

- o Within the first 12 months of treatment: ≥ 25% increase in the product of the greatest perpendicular diameters of the solid component AND ≥ 0.4 cm increase in each of at least two dimensions of the solid component (note that these do not have to be the same measurements used to determine the product of the greatest perpendicular diameters) compared to the smallest disease measurement recorded since the start of protocol OR any new or worsening significant neurologic/vision deficit in conjunction with a lesser change in the solid component OR any new or worsening significant neurologic/vision deficit associated with solely a change in the cystic component that does not at least stabilize following a simple cyst aspiration. Isolated cystic enlargement is not considered progressive disease during the first 12 months of treatment unless more than 1 cyst aspiration is required for symptom control.
- o After the first 12 months of treatment: ≥ 25% increase in the product of the greatest perpendicular diameters of the tumor as a whole (solid and cystic component) AND ≥ 0.4 cm increase in each of at least two dimensions of the tumor as a whole compared to the smallest disease measurement recorded since the start of protocol OR any new or worsening significant neurologic/vision deficit in conjunction with a lesser change in the tumor as a whole. If cyst aspiration is required for symptom control, the patient will be considered to have PD.

Stratum 2:

 \circ Within the first 12 months of treatment: $\geq 25\%$ increase in the product of the greatest

perpendicular diameters of the solid component AND \geq 0.4 cm increase in each of at least two dimensions of the solid component (note that these do not have to be the same measurements used to determine the product of the greatest perpendicular diameters) compared to the smallest disease measurement recorded since the start of protocol OR any new or worsening significant neurologic/vision deficit in conjunction with a lesser change in the solid component. Isolated cystic enlargement in the post- irradiation cohort is not considered progressive disease during the first 12 months of treatment, and it is anticipated that patients may already have or may need an Ommaya reservoir for repeated cyst taps as needed to control symptoms.

o After the first 12 months of treatment: ≥ 25% increase in the product of the greatest perpendicular diameters of the solid component AND ≥ 0.4 cm increase in each of at least two dimensions of the solid component of the tumor compared to the smallest disease measurement recorded since the start of protocol OR any new or worsening significant neurologic/vision deficit in conjunction with a lesser change in the solid component. An isolated increase in the cystic component in an asymptomatic patient is not considered progressive disease. Patients with progressive neurologic signs and/or symptoms associated with isolated cyst formation or progression will be considered to have PD if the neurologic signs and/or symptoms do not improve within 4 weeks of cyst aspiration or if > 2 cyst aspirations are required to control symptoms.

11.1.4 Stable disease (SD):

Those patients don't meet the criteria for PD or response.

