3.1.12 Radiographic Progression

Patients must have evidence of radiographic progression as defined below:

• Stratum 1:

o defined as ≥ 25% increase in the product of the greatest perpendicular diameters of the tumor as a whole (solid and cystic component) AND ≥ 0.4 cm increase in each of at least two dimensions of the tumor as a whole OR any new or worsening neurologic/vision deficit in conjunction with a lesser change in the solid or cystic component.

• Stratum 2:

- o For patients more than 6 months following RT (including radiosurgery or P32), progression is defined as a $\geq 25\%$ increase in the product of the greatest perpendicular diameters of the solid component AND ≥ 0.4 cm increase in each of at least two dimensions of the solid component;
- o For patients more than 12 months following RT (including radiosurgery or P32), progression is defined as ≥ 25% increase in each of the product of the greatest perpendicular diameters of the solid tumor AND ≥ 0.4 cm increase in each of at least two dimensions of the solid tumor. Patients demonstrating predominantly cystic progression more than 12 months after RT must show a continued increase in the cystic component on two serial MRI scans performed at least 4 weeks apart

OR re-accumulation of the cyst following one or more cyst aspirations. Patients with progressive neurologic signs and/or symptoms associated with isolated cyst formation or progression are eligible if the neurologic signs and/or symptoms do not improve within 4 weeks of cyst aspiration.

3.1.13 Pregnancy Status:

Female subjects of childbearing potential must not be pregnant or breast-feeding. Female subjects of childbearing potential must have a negative serum or urine pregnancy test. (Pregnancy test must be repeated within 72 hours prior to the start of therapy).

3.1.14 Pregnancy Prevention:

Subjects of childbearing or child fathering potential must be willing to use a medically acceptable form of birth control, which includes abstinence, while being treated on this study.

3.1.15 Informed Consent:

Ability to understand and the willingness to sign a written informed consent document

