9.3.2 Outcome Measure

See section 11 for the linear parameters used to assess response, depending on the stratum and whether the tumor is predominantly solid or cystic or both.

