Kaplan-Meier estimates of distributions of PFS for all eligible patients who receive at least one dose of PI will be provided separately for each stratum. PFS will be measured from the date of initial treatment to the earliest date of disease progression, second malignancy or death for any reason for patients who fail; and to the date of last contact for patients who remain at risk for failure.

Both for objective response assessments as well as PFS calculations, the assessments made at the treating site will be used. Any discrepancies between the treating sites' assessments and the central review will be recorded and described.

Toxicity data will be summarized via frequency tables both for episodes and for number of patients separately for each stratum. We will also tabulate the data related to dose reductions and treatment discontinuation due to toxicity.

Analysis Plan for Central Imaging Review:

All imaging studies obtained during the first year of treatment in Stratum I as well as all scans with the smallest disease measurement recorded since the start of protocol and scans documenting objective response or progressive disease in both strata will be centrally reviewed at the end of the study. We will summarize any discordance between site's assessment and the central review across patients within a stratum as well as on a per patient basis taking into account the longitudinal data that will be available especially in Stratum I. Specific attention will

be given to PD assessment as we anticipate that there will be cases where PD criteria will be satisfied based on protocol definition but not by MacDonald criteria and vice-versa.

Analysis Plan for the WNT pathway activation data:

We will summarize the frequency of nuclear beta-catenin by IHC in FFPE tumor sections. We will also explore associations between presence of nuclear beta-catenin and outcome. Separately in each stratum, if we observe 10 or more responses among patients from whom biology data are available, we will use exploratory logistic regression models to look for associations between biological markers and response. Similarly, if we observe 10 or more progressions among patients from whom biology data are available in a stratum, we will explore associations between biological markers and PFS. Otherwise association with response and PFS will be summarized descriptively.

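### Stratum 2 response is measured on the whole tumour, cyst included, and no rule says how a scan taken after a cyst tap counts, so drainage can be scored as a primary-endpoint response

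*Combined protocol and SAP*

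**What the plan says.** - **Response (11.1.2).** PR in both strata is at least a 50% "decrease in the product of the greatest perpendicular diameters of the tumor as a whole, i.e., solid and cystic components", sustained on a scan 3 months later. No reference scan is named.
- **Stratum 2 primary endpoint (13.1).** "Sustained Objective Response (PR+CR) rate in the cystic and/or soft tissue component observed during the first year of treatment". Section 13.3 adds that "objective responses observed during the first year must be sustained for 3 months".
- **Taps in that year (11.1.3, Stratum 2, first 12 months).** Isolated cyst enlargement is not progressive disease (PD), and "it is anticipated that patients may already have or may need an Ommaya reservoir for repeated cyst taps as needed to control symptoms". No number is given.
- **Where aspiration has rules.** Eligibility (3.1.12) admits, among others, patients with "re-accumulation of the cyst following one or more cyst aspirations". The PD definitions (11.1.3) count aspirations in Stratum 1; in Stratum 2 they do so only after 12 months ("if > 2 cyst aspirations are required to control symptoms"). The CR and PR definitions do not mention aspiration.
- **Whose assessment counts (13.3, Analysis Plan).** "Both for objective response assessments as well as PFS calculations, the assessments made at the treating site will be used". Differences from central review are recorded and described.
- **What is measured.** 13.1 refers to the cystic and/or soft tissue component and 11.1.2 to the whole tumour. 9.3.2 says the linear parameters vary "depending on the stratum and whether the tumor is predominantly solid or cystic or both", but the CR and PR text does not vary.

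**The concern.** A tap shrinks the measured quantity directly, whether or not the drug works. The plan recognises that aspiration affects outcome scoring, because it writes aspiration rules into the PD definitions. It writes none for response, although response includes the cyst and is counted in the year when repeated taps are anticipated. Applied exactly as written, the PR definition counts a drained cyst that is small on both the response scan and the confirmation scan.

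The Stratum 2 go/no-go decision is at stake. It turns on a handful of patients, so one response can settle it. Without tap dates and a prespecified check, a reader of a 4-of-19 result could not tell whether it depends on a drained cyst.

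**Working it through.** **1. The plan's own figures.** Inputs from 13.3, Stratum 2: 11 patients in stage 1, stop if 1 or fewer respond; 19 in total, active if 4 or more respond; null rate 10%, target rate 35%. With X1 ~ Bin(11, p) and X2 ~ Bin(8, p):

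- P(stop early) = P(X1 ≤ 1)
- P(active) = Σ over x ≥ 2 of P(X1 = x) · P(X2 ≥ 4 − x)

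At p = 0.10:

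- P(stop early) = 0.697 (plan: 70%).
- P(active) = 0.2131 × 0.1869 + 0.0710 × 0.5695 + P(X1 ≥ 4), which is 0.0398 + 0.0405 + 0.0185 = 0.0988 (limit 0.10).

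At p = 0.35, P(stop early) = 0.061 (plan: 6%) and P(active) = 0.909 (plan: 90%). The design arithmetic is correct. The gap is in the endpoint definition.

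**2. How much one response matters.** P(exactly 4 of 19 and declared active) is 0.0657 at p = 0.10 and 0.0748 at p = 0.35. As a share of trials declared active, that is 0.0657 / 0.0988 = 66% at a true rate of 10%, and 0.0748 / 0.9086 = 8% at 35%.

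**3. Effect of drainage scored as response.** Let t be the true sustained response rate and q the share of true non-responders scored PR through drainage. The documents give no value for q, so it is an assumption. The apparent rate is p = t + (1 − t)q; for example, t = 0.10 and q = 0.05 give 0.10 + 0.90 × 0.05 = 0.145.

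| True rate t | q = 0 | q = 2% | q = 5% | q = 10% | q at which P(active) passes 10% |
|---|---|---|---|---|---|
| 10% | 9.9% | 15.5% | 25.7% | 45.0% | about 0.05% |
| 5% | 1.1% | 3.2% | 9.2% | 25.7% | about 5.3% |
| 0% | 0% | 0.04% | 1.1% | 9.9% | about 10.0% |

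At t = 10% the early-stopping probability falls from 69.7% to 51.1% at q = 5% and 35.3% at q = 10%. The 0.05% crossing mainly reflects that 0.0988 already sits next to the limit.

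**4. Bias in the other direction.** A baseline taken soon after drainage may refill, and cysts may enlarge temporarily on interferon (2.2.1, 11.1.3). If a share m of true responders is missed, p = t(1 − m) + (1 − t)q. With t = 10% and m = 20% (assumption), p = 0.08 + 0.90q, and P(active) is 5.1%, 9.3% and 18.0% at q = 0, 2% and 5%.

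**5. Whether existing safeguards close the gap.**

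- The 3-month confirmation removes one tap followed by refilling. It does not address a tap between the two scans or a cyst that stays collapsed.
- Separate solid and cystic measurements (11.1), central review of response scans (9.3.4) and the planned volumetry (2.5.2) can show that only the cyst shrank. They cannot show that a tap caused it, and they do not override the site assessment.

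**The case against.** The strongest case is that the route is narrow.

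- Predominantly cystic patients can enter Stratum 2 because the cyst refilled after aspiration, and such cysts are less likely to stay collapsed for 3 months.
- Taps for symptoms tend to follow enlargement, and draining a cyst back towards its entry size is not a 50% fall.
- Stratum 2 also admits solid progression, where draining a minor cyst cannot halve the whole-tumour product. If 30% to 50% of non-responders were cyst-dominant (assumption), q = 5% would need 5/50 = 10% to 5/30 = 17% of them to show a drainage-maintained fall on both scans.
- Sensitivity to one response belongs to any 19-patient design. The 66% is conditional on a false positive; unconditionally the figure is 6.6%.
- Sites must know about aspirations to apply the eligibility and PD rules, and the data form, which is not in the documents, may already record them.
- The wording of 13.1 suggests that cyst shrinkage was meant to count.

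Most of this stands as a limit on size: q may be small, and the net direction is uncertain. It does not remove the mechanism. Other cystic entry routes exist, and repeated reservoir taps are the situation the plan itself anticipates. Recording taps would still leave their scoring undefined. Counting cyst shrinkage as response is legitimate, but drug effect and drainage then need to be told apart. Naming the reference scan and aligning the wording are editorial and add nothing to the weight of the point.

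**Conclusion.** The concern holds and should be fixed. The Stratum 2 primary endpoint can count cyst drainage as partial response, because no rule covers scans after a tap and the site assessment governs. Confidence is high for the missing rule only.

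The size is unknown. The documents available for this review, which lack part of Section 2.3, give no tap rate or cystic fraction, so every value of q and m is an assumption. The effect matters mainly for a drug near the 10% null rate. For a drug with a true rate of 5% or 0%, the error limit is passed only when q exceeds about 5% or 10%.

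**What to change.** None of these changes when or how taps are done.

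1. Record the date of every Stratum 2 cyst aspiration, shortly before baseline and during year 1, if the data form does not already hold it.
2. Keep the primary analysis, and prespecify a sensitivity analysis of the stage 1 count and the 4-of-19 decision. A whole-tumour responder with an aspiration between the reference and confirmation scans counts as a non-responder unless the solid component also meets the 50% criterion. Report it beside the primary result, with the number of patients tapped shortly before baseline.
3. Name the PR reference scan in 11.1.2.
4. Reconcile 13.1, 11.1.2 and 9.3.2 on which component defines response.

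**Cost.** At most one data item and one small analysis. No extra MRI is needed, since solid measurements are already required. The primary test keeps 90.9% power at a 35% rate.

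The sensitivity analysis is stricter and can reclassify a genuine cystic responder who was tapped during temporary enlargement. If it reclassified 5%, 10%, 20% or 30% of true responders (assumption), the rate would be 0.35 × (1 − share) = 0.3325, 0.315, 0.28 or 0.245. The chance of meeting both thresholds would then be 88.3%, 85.2%, 77.2% or 66.5%. Falling below 4 there is a caution, not proof of inactivity.
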